4.1 Sample Size

Approximately 720 subjects with 60 subjects per study group will be enrolled in the study. Approximately half of enrolled subjects will be selected to provide a blood sample for PBMC collection.

The number of subjects proposed to be enrolled in this protocol is based upon previous experience with similar studies such as the Mix and Match Studies (NCT 01317745 and NCT 01217758) performed by Division of Microbiology and Infectious Diseases/National Institute of Allergy and Infectious Diseases. These prior studies had study groups of similar size that proved to be sufficient to allow the collection of meaningful data, especially with respect to acute solicited AEs and antibody results. While the current study is not designed to test specific hypotheses, Table 4-2 and Table 4-3 indicate the power of the proposed sample size to detect a range of common, immediate postvaccination elicited safety events as well as to meet the success criteria for SPR.

Table 4-2Safety - Power for Detecting at Least 1 Serious Adverse Event (SAE)
or Medically-Attended Adverse Event (MAAE) or a Grade 3 Solicited
Adverse Event (AE)

True Event Rate (%)	Power (%) N = 60	Power (%) N = 120
0.1	5.8	11.3
0.5	26.0	45.2
1	45.3	70.1
2	70.2	91.2
3	83.9	97.4
4	91.4	99.3
5	95.4	99.8

Note: The exact method was used for the calculations in this table.

Table 4-3Immunogenicity - Power for Meeting Success Criteria of
Seroprotection Rate (SPR)

Success Criteria (%)	Proportion of Subjects Achieving a Serum HAI Antibody Titer of at Least 1:40 for the Testing Vaccine (%)	Power (%) N = 60	Power (%) N = 120
	90	98.5	>99.9
70	85	81.9	99.0
	80	44.9	79.0

4.2 Randomization, Stratification, and Blinding

4.2.1 Randomization

Subjects will be randomly assigned to 1 of 12 study groups stratified by site. An Interactive Response Technology (IRT) will be used to administer the randomization schedule centrally. Biostatistics will generate the randomization schedule using SAS® software Version 9.3 or later (SAS Institute Inc, Cary, North Carolina) for IRT, which will link sequential subject randomization numbers to treatment codes. The randomization schedule will be created by the dedicated randomization team, stored in a separate project area, and will be blinded to the project team.

4.2.2 Stratification

Randomization is stratified by site to balance treatment assignments over the course of the trial within each site.

4.2.3 Blinding

This is a double-blind study. All IP will be prepared and administered by an unblinded study staff member. IP accountability will be monitored by a separate unblinded monitor. All other persons involved in the study will be blinded to study group assignment, including the study staff observing the subject after vaccination and the subject. Until the final database lock and

unblinding, all unblinded data analyses will be handled by the unblinded team of statisticians and programmers. A strict firewall between the blinded and unblinded teams will be maintained.

For the 2 planned interim analyses, BARDA, site personnel, and subjects will be unblinded for all interim data at Day 43 and Day 163 only at the study group level (i.e., data will be provided with each group having a fake designation). For the final analysis, all parties will be unblinded to all data at the subject level at Day 142 for all Groups A-L and Day 262 for Groups E, F, K and L.

With the exception of the unblinded study staff who administer the IP and a separate unblinded monitor who will monitor IP accountability, all other study staff are to remain blinded until CSR database freeze and a formal unblinding is scheduled. The members of the IDMC will review subject level unblinded safety data on an ad hoc basis when the Study Pausing Rules (Section 11.1) are met. A separate unblinded team will handle any ad hoc production of unblinded tables, listings, and figures for ad hoc IDMC meetings. Blinded individuals will not be made aware of any unblinded data provided to the IDMC.

4.3 Analysis Sets

4.3.1 All Enrolled Population

The All Enrolled Population will consist of all subjects who signed the informed consent form (ICF).

4.3.2 Full-Analysis Set (FAS)

The FAS will consist of all subjects who are randomly assigned to receive IP. All analyses using the FAS will group subjects according to randomized treatment.

4.3.3 Safety Set

The safety set will consist of all subjects who are randomly assigned and receive at least 1 dose of IP. Safety endpoint summaries and listings will be performed on the safety set using study group treatment actually received.

4.3.4 Immunogenicity-Full Analysis Set (IFAS)

The IFAS will consist of all subjects who are randomly assigned, receive at least 1 dose of IP, and have at least 1 valid postvaccination and determinate assay result. As supportive analysis, all the immunogenicity endpoint summaries will be performed on the IFAS by actual treatments received.

4.3.5 Immunogenicity Per-Protocol Set (IPPS)

The IPPS is a subset of the IFAS, where all subjects meet the IFAS criteria and must meet the following criteria:

- have received a full dose of IP at all planned dosing visits.
- have received all the doses of IP to which they were randomly assigned.
- have no significant protocol deviations that are determined to potentially interfere with the immunogenicity assessment of IP.

- have received Visit 4 (Day 22) vaccination within -3 to +10 days of the expected visit date (21 days from Day 1) for all Groups, and Visit 8 (Day 142) vaccination within ±14 days of the expected visit date (141 days from Day 1) for Groups E, F, K and L.
- have Visit 7 (Day 43) immunogenicity sample collected within -3 to +10 days of the expected visit date (21 days f rom Visit 4 [Day 22]) for Groups A-D and G-J, and Visit 11 (Day 163) immunogenicity sample collected within -3 to +10 days of the expected visit date (21 days from Visit 8 [Day 142]) for Groups E, F, K and L.

All the immunogenicity endpoint summaries will be performed primarily on the IPPS using treatment actually received.

5 Subject Disposition

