BARDA CSN Protocol: BP-I-16-005 Version 2.0

All IP will be prepared and administered by an unblinded staff member. The study staff observing the subject after vaccination and the subject will be blinded to group assigned.

Subject completion is defined as completing all study visits through Visit 9 (end-of-study visit) for Groups A-D and G-J (Table 12–1) or Visit 14 (end-of-study visit) for Groups E, F, K, L (Table 12–2). Approximately half of enrolled subjects per study group will be selected to provide a blood sample for PBMC collection. A select number of sites will have capability for PBMC collections, and only subjects enrolled at those sites will contribute to the PBMC subset. Subjects who participate in this study will be asked to consent to be contacted with a request to participate in future clinical studies of subjects who have been vaccinated against influenza H5, such as longer interval prime-boost studies.

No formal independent data monitoring committee (IDMC) meetings are planned for this study. The IDMC will meet only if a pausing rule is met.

Two interim analyses are planned based on cumulative immunogenicity and safety data after all subjects complete Day 43 and all subjects complete Day 163. At each time point, the study database will be monitored, cleaned, and frozen through the data cut time point. Safety and immunogenicity data will be summarized by study group. Interim analysis results will be unblinded at the group level, and each group will be assigned a fake name. Results will be provided to the sponsor with groups identified only by their fake names.

A single clinical study report (CSR) will be written with unblinded data at the subject level after Groups E, F, K, L have completed Day 262. Additional safety results from the time of CSR database freeze until the end-of-study visit for all groups will be included in an addendum to the final CSR.

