8.2 Secondary Analysis

- Geometric mean titers (GMTs) of HAI antibody responses against each strain vaccinated at Day 1, 22, 43, and 142 visits (Groups A-D, G-J) and Day 1, 22, 43, 142, 163 and 262 visits (Groups E, F, K and L) and asymptotic 95% CIs will be summarized along with other descriptive statistics, including number of subjects, geometric standard deviation, minimum, maximum, and median for each treatment group. Line plots will be provided for GMT of HAI and corresponding 95% CI for all visits.
- GMTs of MN antibody responses against each strain vaccinated at Day 1, 22, 43, and 142 visits (Groups A-D, G-J) or Day 1, 22, 43, 142, 163 and 262 visits (Groups E, F, K and L) and asymptotic 95% CIs will be summarized along with other descriptive statistics, including number of subjects, geometric standard deviation, minimum, maximum, and median for each treatment group. Line plots will be provided for GMT of MN and corresponding 95% CI for all visits.
- SPR for HAI antibody responses against each strain vaccinated at Day 1, 22, 43, and 142 visits (Groups A-D, G-J) or Day 1, 22, 43, 142, 163 and 262 visits (Groups E, F, K and L) along with asymptotic 95% CIs will be summarized. SPR for the combinations of HAI antibody responses against multiple strains vaccinated will be also summarized for each treatment group. Line plots will be provided for SPR for HAI and corresponding 95% CI for all visits.
- SCR for HAI antibody responses against each strain vaccinated at Day 22, 43, and 142 visits (Groups A-D, G-J) or Day 22, 43, 142, 163 and 262 visits (Groups E, F, K and L) with asymptotic 95% CIs will be summarized for each treatment group. Line plots will be provided for SCR for HAI and corresponding 95% CI for all visits.
- SCR for MN antibody responses against each strain vaccinated at Day 22, 43, and 142 visits (Groups A-D, G-J) or Day 22, 43, 142, 163 and 262 visits (Groups E, F, K and L) with asymptotic 95% CIs will be summarized for each treatment group. Line plots will be provided for SCR for MN and corresponding 95% CI for all visits.

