8.3 Exploratory Analysis

Exploratory analyses will be performed to compare immunogenicity endpoints between specified study groups. All exploratory analyses will be performed by treatment received based on IPPS. The following group-wise (targeted group vs. reference group) comparisons will be performed for GMT and SPR of HAI antibody responses:

• For strain A/gyrfalcon/Washington/41088-6/2014 H5N8 (Seqirus) on Day 43:

Study Group A vs. Study Group E

Study Group B vs. Study Group E

Study Group C vs. Study Group E

Study Group D vs. Study Group E

Study Group F vs. Study Group E

Study Group G vs. Study Group K

Study Group H vs. Study Group K

Study Group I vs. Study Group K

Study Group J vs. Study Group K

Study Group L vs. Study Group K

 For strain A/barheaded goose/Qinghai Lake/1A/2005 (H5N1) (Sanofi Pasteur) on Day 163: Study Group E vs. Study Group F

Study Group K vs. Study Group L

The logarithms of HAI antibody titers will be compared by two-sided Student's t-test between above specified study groups. Geometric mean ratio estimate will also be presented for each pair of group comparison with corresponding asymptotic 95% CIs and p-values based on two sample t-test.

The difference in proportions (SPR for targeted group-SPR for reference group) between the above specified study groups will be presented along with corresponding asymptotic 95% CIs and p-values based on Chi-square test.

Based on actual results, additional exploratory study group comparisons may be performed.

9 Safety Analysis

All safety evaluations will be performed using the Safety Set.

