9.6 Pregnancy

Urine pregnancy test results for the Safety Set will be included in a data listing containing all subject-level data collected in the eCRF.

10 Interim Analysis

Interim analyses will be performed based on cumulative immunogenicity and safety data at Day 43 and Day 163 for all study groups. At each time point the study database will be monitored, cleaned, and frozen. The study team, except the unblinded team members, should remain blind until final database lock and unblinding. Interim analysis results will be unblinded at the group level and provided to BARDA by the unblinded team. A selection of safety and immunogenicity analyses in section 5 to section 9 will be included in the interim analyses. Interim data will be presented in tables, listings and figures.

11 Ad Hoc Safety Analysis for Independent Data Monitoring Committee (IDMC)

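### One per-protocol set serves every visit: Day 22, 43 and 142 results in Groups E, F, K and L depend on dose 3 and a Day 163 sample, and 8 of 12 exploratory comparisons use unequal entry rules

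*SAP*

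**What the plan says.** SAP 4.3.5 gives one IPPS definition with no version by visit and makes it the main set for all immunogenicity summaries. Every subject must "have received all the doses of IP to which they were randomly assigned". The remaining timing rules differ by regimen:

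- Groups A-D and G-J: dose 2 in window and a Day 43 sample within -3 to +10 days.
- Groups E, F, K and L: dose 2 in window, "Visit 8 (Day 142) vaccination within ±14 days of the expected visit date", and "Visit 11 (Day 163) immunogenicity sample collected within -3 to +10 days of the expected visit date". There is no IPPS window for their Day 43 sample.

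Protocol 7.5 has the same split: a valid HAI result at Day 43 for the two-dose groups and at Day 163 for the three-dose groups.

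SAP 8.2 summarises the three-dose groups at Days 1, 22, 43, 142, 163 and 262. SAP 8.3 states: "All exploratory analyses will be performed by treatment received based on IPPS". SAP 8 names the IFAS as the supportive set, then limits SCR and GMT to the IPPS alone. On the interim analyses, SAP 10 says only: "A selection of safety and immunogenicity analyses in section 5 to section 9 will be included in the interim analyses". Protocol 3.1 adds: "At each time point, the study database will be monitored, cleaned, and frozen through the data cut time point".

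**The concern.** A Day 43 result should not depend on whether the subject later receives dose 3 or attends Visit 11. Through Day 43 all twelve groups have the same visits and two doses, so nothing in the design requires different entry rules at that point. E and K are each the shared reference for five Day 43 comparisons, so any distortion in either carries into all the comparisons that use it.

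The later selection need not be random. Protocol 4.3 lists reasons for not revaccinating that include adverse events, liver enzyme elevations, intercurrent illness and pregnancy. The restriction on nonstudy vaccines runs to 21 days after the last dose. That is nominally Day 43 in the two-dose groups and Day 163 in the three-dose groups, so the latter have about 120 more days in which a deviation can remove them.

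The SAP 8.3 comparisons carry p-values and are the only between-group analyses the SAP specifies. They bear on the question in the protocol introduction of whether antigen choice and sequence matter. With SCR and GMT held to the IPPS, those results and all MN results would also lose the wider-set check that protocol 7.5 promises.

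**Working it through.** The documents give no figure for the size of this effect. The check is a count of comparisons, a date calculation and an assumption-based range.

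**1. Comparisons (SAP 8.3).**

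| Time point | Pairs | Number | Same IPPS rule in both arms? |
|---|---|---|---|
| Day 43 | A, B, C, D vs E | 4 | No |
| Day 43 | G, H, I, J vs K | 4 | No |
| Day 43 | F vs E; L vs K | 2 | Yes, both conditioned on later events |
| Day 163 | E vs F; K vs L | 2 | Yes, rule matches the time point |

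Total 4 + 4 + 2 + 2 = 12; unequal 4 + 4 = 8. All ten Day 43 comparisons are conditioned on later events in at least one arm. The asymmetry also runs the other way: a Day 43 sample outside the IPPS window removes an A-D or G-J subject, but removes an E or K subject only if it is judged an interfering significant deviation.

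**2. Distance from the Day 43 sample to the later criteria (nominal days).** Dose 3: 142 - 43 = 99 days. Day 163 sample: 163 - 43 = 120 days.

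**3. Qualification at a Day 43 cut (SAP 4.3.5 windows).**

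- Earliest qualifying dose 3: 142 - 14 = Day 128.
- Earliest qualifying Day 163 sample: 128 + 21 - 3 = Day 146.
- Latest in-window Day 43 sample: dose 2 at 22 + 10 = Day 32, then 32 + 21 + 10 = Day 63.

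Since 146 > 63, no E, F, K or L subject meets the definition on data through Day 43. That is 4 of 12 groups, or 4 × 60 = 240 of 720 planned subjects. If the cut is instead a calendar date, early enrollees could qualify once enrolment exceeds about 146 - 43 = 103 days. Enrolment duration is not given.

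**4. Possible shift in a three-dose group's Day 43 SPR.** No dropout rate is given, so the loss and the SPR gap below are assumptions.

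Shift = fraction lost × (SPR in kept − SPR in lost).

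| Lost after Day 43 | Subjects of 60 | 10-point gap | 20-point gap |
|---|---|---|---|
| 5% | 3 | 0.5 | 1.0 |
| 10% | 6 | 1.0 | 2.0 |
| 20% | 12 | 2.0 | 4.0 |

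**5. Precision for scale (95%, n = 60 per group).**

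- One group: 1.96 × √(0.8 × 0.2/60) = 10.1 points at SPR 80%; 1.96 × √(0.5 × 0.5/60) = 12.7 points at SPR 50%.
- Difference between two groups: 1.96 × √(2 × 0.16/60) = 14.3 points; 1.96 × √(2 × 0.25/60) = 17.9 points.

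**6. GMT and SCR set, side by side.** SAP 4.3.4 and protocol 7.5 put all immunogenicity endpoint summaries on the IFAS as supportive analysis, and the opening of SAP 8 agrees. Later in SAP 8, SCR and GMT are confined to the IPPS. SAP 13 lists only the two omitted exploratory objectives, so this departure is not declared.

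**The case against.** Five points can be made for the plan.

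- **The split comes from the protocol.** Protocol 7.5 already defines the IPPS this way. That is true, so the remedy departs from a protocol-defined set and must be declared. It does not make the Day 43 comparisons like for like.
- **A fixed completer cohort suits within-group time courses.** The SAP 8.2 line plots would otherwise show different subjects at each visit. This stands as a legitimate choice for those plots. It does not justify unequal rules between arms in SAP 8.3.
- **The empty interim set is conditional.** SAP 10 names no analysis set, SPR can be shown on the IFAS, and a calendar cut could admit early enrollees. This stands. What remains is that SAP 10 should name the set: on one reading the three-dose groups are empty, and on the other they hold only early enrollees.
- **The effect is small and assumed.** The largest shift in the assumed range, 4 points, is under a third of the two-group half-width of 14 to 18 points. The comparisons are exploratory in a descriptive study. This limits the severity. The effect on GMT and MN has not been estimated.
- **The GMT and SCR conflict is a separate defect.** It is, and which passage prevails is unresolved. Individual results are listed on the IFAS, but a listing does not replace the promised summaries.

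**Conclusion.** The concern holds and should be fixed. Eight of the twelve SAP 8.3 comparisons apply different entry rules to the two arms. The Day 22, 43 and 142 IPPS summaries in Groups E, F, K and L depend on later events. These are exact readings of the text. That no three-dose subject can qualify at the first interim holds if data are cut at study Day 43, and is conditional otherwise. The bias range of 0.5 to 4 SPR points rests wholly on the assumed 5-20% loss and 10-20 point gap.

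The primary endpoint is not affected, because each group's IPPS rule matches its own primary time point. The per-group SPR summaries keep their IFAS analysis; the SAP 8.3 comparisons do not. The contradiction over the set for GMT and SCR stands whatever the size of the bias.

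**What to change.** In SAP 4.3.5, define the IPPS by time point, using only criteria met up to the sample analysed and no interfering significant deviation to that date:

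- **Day 22:** dose 1 as randomised and a valid Day 22 sample.
- **Day 43, all twelve groups:** doses 1 and 2 as randomised, Visits 4 and 7 within the existing IPPS windows, and a valid Day 43 HAI result.
- **Day 142 (before dose 3 in E, F, K and L):** the two-dose criteria and a valid Day 142 sample.
- **Days 163 and 262:** the current three-dose criteria.

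Use the Day 43 set for the ten Day 43 comparisons and the Day 43 interim, and name it in SAP 10. Unequal comparisons then fall from 8 of 12 to 0 of 12. If a fixed completer cohort is wanted for the line plots, keep it for that purpose and label it so.

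In SAP 8, remove the restriction of GMT and SCR to the IPPS so that both are also run on the IFAS, and repeat the SAP 8.3 comparisons on the IFAS. Record the changed set definition in SAP 13, since protocol 7.5 has the same split.

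The cost is SAP wording, extra set flags and repeat tables. No new data are needed, and the power figures in SAP Table 4-3 do not change.

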5.1 Disposition

The number and percentage of subjects who were randomized, completed Day 142 visit or did not complete Day 142 visit (including reason for not completing Day 142 visit) for groups A-D, G-J and completed Day 262 visit or did not complete Day 262 visit (including reason for not completing Day 262 visit) for groups E, F, K and L, and treated according to each dose will be summarized by randomized treatment and overall based on the FAS. A similar summary by site will also be provided.

A corresponding listing will be provided with subject-level data including randomization status, Day 142 visit completion/discontinuation status, date, and reason for not completing Day 142 visit (if applicable) and Day 262 visit completion/discontinuation status, date, and reason for not completing Day 262 visit (if applicable).

The disposition table for the addendum will include summary of number and percentage of subjects who completed or discontinued study along with primary reason for study discontinuation.

5.2 **Protocol Deviations**

Protocol deviations will be summarized by categories, randomized treatment and overall based on FAS. Additionally, the number and percentage of subjects with at least one protocol deviation and the number and percentage of subjects with at least one significant protocol deviation will be summarized. A significant deviation occurs when there is nonadherence to the protocol by the subject or investigator that results in a significant, additional risk to the subject or risk to validity of study outcomes. Significant deviations can include nonadherence to inclusion or exclusion criteria or nonadherence to Food and Drug Administration (FDA) regulations or ICH GCP guidelines, and may lead to the subject being withdrawn from the study. Significant deviations will be identified based on blinded data reviews of the deviation log throughout the study and will be finalized prior to database lock. Significant deviations will be summarized by categories, randomized treatment and overall based on FAS. A corresponding listing will be presented.

6 Demographics and Baseline Characteristics

The following demographic and baseline characteristics will be summarized using the Safety Set, IPPS and IFAS by treatment received. In the event that a subject incorrectly receives doses of IP different from group A-L regimen, the subject will be included in the listings. A separate summary by site based on Safety Set will also be provided.

6.1 Demographics

Continuous Variables:

- Baseline age (years) from subject age entered directly in IVRS at Visit 1
- Height (in)
- Weight (lb)
- Body mass index (BMI) (kg/m²)

Specifications for computation:

• BMI $(kg/m^2) = weight (lb)*703/[height (in)]^2$

Categorical Variables:

- Baseline age (years) 18-<30, 30-<40, and 40-49
- Sex (Male, Female)
- Race (White, Black or African American, Asian, American Indian or Alaska Native, Native Hawaiian or Other Pacific Islander, Other, and Multi-racial)
- Ethnicity (Hispanic or Latino, and Not Hispanic or Latino)
- Subject travelled outside the United States after 2005 (Yes, No)
- Subject lived outside the United States for 3 months or more after 2005 (Yes, No)
- A corresponding listing will be provided with subject-level demographic data. The summary of vaccines received 12 months prior to Visit 1 will also be included in a data listing.

